The following variables of interest were chosen as either due to known association with risk of developing severe COVID-19 and/or known associations with neuropsychological disease. Distributions of each variable will be summarised by cohort using descriptive statistics.

Demographics (Aims 1 & 2)

- Age
- Gender
- Material deprivation by quintile of Townsend deprivation score

- Ethnicity (White, Indian, Pakistani, Bangladeshi, other Asian, Black African, Chinese, and other ethnic group),
- Geographical region
- Domicile (homeless, care home residence, neither)
- Household size

Lifestyle (Aims 1 & 2)

- Body mass index (BMI)
- Smoking status (non-smoker, ex-smoker, light smoker: 1–9 cigarettes/day, moderate smoker: 10–19 cigarettes/day, heavy smoker: ≥20 cigarettes/day, not recorded)
- Alcohol intake (none, trivial: <1 unit/day, light: 1–2 units/day, medium: 3–6 units/day, heavy: 7–9 units/day, very heavy: >9 units/day, not recorded).

Co-morbidities (Aims 1 & 2)

- Cardiovascular diseases coronary heart disease, stroke/transient ischaemic attack, atrial fibrillation, congestive cardiac failure, thromboembolism, peripheral vascular disease, congenital heart disease, hypertension
- Respiratory diseases asthma, chronic obstructive pulmonary disease, rare lung conditions (bronchiectasis, cystic fibrosis, alveolitis), pulmonary hypertension or pulmonary fibrosis
- Endocrine diseases type 1 and 2 diabetes, hypothyroidism
- Chronic kidney disease
- Neurological conditions- epilepsy/seizures, Parkinson's disease, motor neurone disease, multiple sclerosis, myasthenia gravis, Huntington's disease
- Cancer blood cancer, respiratory tract cancer, and other relevant cancer
- Bone and joint conditions- osteoarthritis, rheumatoid arthritis or Systemic Lupus Erythematosis (SLE), osteoporosis, osteoporotic fracture (hip, spine wrist, humerus)
- Gastrointestinal diseases liver disease, liver cirrhosis
- Transplants solid organ transplant (excluding kidney and bone marrow), bone marrow or stem cell transplant
- Sickle cell disease or severe immunodeficiency
- Traumatic brain injury
- Learning disability/Down's syndrome, cerebral palsy

Medications/treatments (Aims 1 & 2)

- antihypertensive drugs,
- aspirin,
- statins,
- Anticoagulants,
- non-steroidal anti-inflammatory drugs,
- bisphosphonates,
- oral contraceptives,
- hormone replacement therapy,

- anticonvulsants
- chemotherapy
- radiotherapy
- immunosuppressant medication
- leukotriene or long-acting beta-agonist

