- oral steroids

Intensive care stay (Aim 2)

- Length of stay
- Duration of advanced respiratory support (invasive ventilation)
- Use of sedation in the first 24 hours of admission

Effect Modifiers

For aim 1, we assessed these potential confounders by creating directed acyclic graphs (DAG) to determine which variables were likely to be to some extent caused by the presence of prior neuropsychological disorders (as the exposure of interest), and which were not likely to be caused by the presence of prior neuropsychological disorders, but were thought to be independently potential predictors of severe Covid outcomes.

Variables from the above list to be included in the model are all those grouped under: demographics; co-morbidities; lifestyle factors; plus prescription of any immunosuppressants and/or anticoagulants. Other medications (as these are not believed to affect the risk of severe Covid outcomes), and in-hospital factors (length of stay and use of sedation during intensive care admission, as these are outcomes potentially caused by Covid severity) will not be adjusted for.

For aim 2, our exposure of interest is admission to intensive care with SARI (compared to admission to intensive care with SARI. This exposure occurs at a fixed time which is used as the baseline for our time to event analysis in predicting the outcome of interest, and all other variables listed above are measured before this baseline. Therefore (depending on the available sample size and number of events), all the previously listed covariates of interest may be included in our adjusted models.

Data sources

Intensive Care Unit admission data will come from the ICNARC CMP dataset Hospital admission and mortality will come from the HES dataset

All exposures and confounders and neuropsychological outcomes will come from the QResearch database.

COVID-19 infection test status will come from the national registry of COVID-19 RT-PCR positive test results from Public Health England (PHE).

Bias

To limit the possible impact of COVID-19 testing bias (collider bias) we will analyse the entire QResearch eligible population, rather than restricting analysis to only those with a positive COVID-19 test.

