Royston Parmar flexible parametric survival models will be used to estimate the hazard ratio of severe COVID-19 outcome (hospital or critical care admission and death) in cohort 1 for patients with neuropsychological disease at study entry compared with those without disease, and for individual neuropsychological diseases and treatments.

This analysis will be adjusted for the listed covariates. The age variable will be included as a restricted cubic spline rather than a linear term. Before commencing analysis, we will assess the numbers of patients with each comorbidity, and may if necessary group the presence of certain less common comorbidities together. Any such grouping will be done on the basis of clinical similarities only and prior to examining any outcomes by comorbidity. We may also include a time-varying binary covariate to record any new diagnosis and/or treatment which occurs after study entry in patients originally free from both diagnosis and treatment, depending on the number of these events. Proportional hazards assumptions will be tested, and time dependent terms will be included if the hazard ratio changes over time (I.e. if the association between neuropsychological disease and risk of severe COVID-19 has changed during the course of the pandemic). A random frailty term will be included to account for similarities amongst patients registered in the same primary care practice. Possible interactions between exposure and age, sex and ethnicity will be considered and tested using a Wald test.

The same methods will be used for secondary analyses in which the main exposure variable will be defined as either the presence of a specific class of neuropsychological disorder or any other neuropsychological disorders or no disorder.

The primary analysis will be used to estimate the hazard ratio of severe SARI outcomes in cohort 2 using the same exposure variables.

If non-proportional hazards are observed in either cohorts 1 or 2, then maximum follow-up time will be capped at 1 year and a time-dependent covariate will be added to the analysis of both cohorts to maintain the comparability of results.

Aim 2.

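### Aim 1 omits oral steroids, chemotherapy, radiotherapy and leukotriene/long-acting beta-agonist drugs for a COVID-only reason, yet the same analysis is used for the SARI cohort

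*Protocol*

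**What the plan says.** The Covariates section of the protocol lists medications for both aims. Chemotherapy, radiotherapy, leukotriene/long-acting beta-agonist drugs and "oral steroids" each have their own entry, separate from "immunosuppressant medication". All listed variables were "chosen as either due to known association with risk of developing severe COVID-19 and/or known associations with neuropsychological disease".

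The Effect Modifiers section then selects the Aim 1 model: "Variables from the above list to be included in the model are all those grouped under: demographics; co-morbidities; lifestyle factors". From the medication list it retains two kinds of drug only, with the wording "plus prescription of any immunosuppressants and/or anticoagulants". Everything else on that list is left out: "Other medications (as these are not believed to affect the risk of severe Covid outcomes". The DAG criterion in the same section also speaks only of predictors of severe COVID outcomes.

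Statistical Methods, Aim 1, says of cohort 1: "This analysis will be adjusted for the listed covariates". For the comparison cohort it says: "The primary analysis will be used to estimate the hazard ratio of severe SARI outcomes in cohort 2 using the same exposure variables". It gives no separate covariate set, and no reason specific to SARI. Objective 3 compares the risk associated with neuropsychological disease between COVID-19 and SARI.

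**The concern.** A variable can be left out of an adjustment set if it is not a cause of the outcome. That has to be argued for each outcome analysed. Here it is asserted for severe COVID only, while the model is also fitted to SARI admission, SARI intensive care admission and death.

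The listing rule sharpens the point. A drug believed not to affect severe COVID was presumably listed for its link with neuropsychological disease, or for an association with COVID that is not thought to be causal. In the first case, if the drug also affects SARI and is not itself a consequence of the exposure, it is a confounder in cohort 2.

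Within cohort 1 the rule is unclear as well. Keeping immunosuppressants accepts that a drug effect on severe COVID is possible through immune suppression. Oral steroids and chemotherapy are separate list entries, so on a plain reading they fall among the dropped drugs. The text does not say whether that is intended.

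At stake are the two cohort-specific hazard ratios and, if any bias differs between cohorts, the Objective 3 comparison. The Introduction itself warns of residual confounding in earlier work on drug classes and respiratory infection.

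**Working it through.** **1. What the text fixes.**

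| Section | What it settles |
|---|---|
| Covariates | Four treatment groups listed for Aims 1 and 2, separately from immunosuppressants |
| Effect Modifiers | All drugs except immunosuppressants and anticoagulants dropped; reason refers to COVID outcomes |
| Statistical Methods, Aim 1 | Adjusts for the listed covariates without repeating the exclusion; same analysis carried to SARI |
| Bias | E-value planned, which addresses unmeasured confounding; these drugs are listed variables |
| Sensitivity analyses | None adds the dropped drugs |

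**2. Size.** The protocol states no figure for this point, so there is nothing to reproduce. For scale only, the bias factor for one omitted binary covariate is

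B = (1 + p1(RR − 1)) / (1 + p0(RR − 1)),

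where p0 and p1 are the drug prevalences without and with neuropsychological disease, and RR is the drug–outcome ratio left after the planned adjustment. All three are assumptions.

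| p0 | p1 | RR | B |
|---|---|---|---|
| 2% | 2.5% | 1.5 | 1.0125/1.010 = 1.002 |
| 2% | 4% | 1.5 | 1.02/1.01 = 1.010 |
| 2% | 4% | 2 | 1.04/1.02 = 1.020 |
| 2% | 6% | 3 | 1.12/1.04 = 1.077 |
| 5% | 15% | 3 | 1.30/1.10 = 1.182 |

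The second to fourth rows give the range of about 1% to 8%. The first row shows what happens if adjustment for the indications shrinks the prevalence contrast. The last is an extreme combination. Over p0 of 1–5%, p1/p0 of 1.25–3 and RR of 1.2–3, B runs from 1.00 to 1.18.

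**3. Against random error.** The 95% confidence limit factor is roughly exp(1.96/√(D·a·(1 − a))), with D events and exposed share a, both assumed.

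- D = 10,000: a = 0.1 gives exp(1.96/√900) = 1.068; a = 0.3 gives exp(1.96/√2,100) = 1.044.
- D = 100,000: a = 0.1 gives exp(1.96/√9,000) = 1.021; a = 0.3 gives exp(1.96/√21,000) = 1.014.

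A bias of 1.02 is therefore well inside the random error at 10,000 events and comparable with it at 100,000. Study Size gives about 8.3 million adults but no event count for Aim 1.

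**4. Objective 3.** If a drug had the same RR and prevalences in both cohorts, B would cancel in the ratio of hazard ratios. If, as the protocol believes, RR = 1 for COVID, while RR = 1.5–3 for SARI with p0 = 2% and p1 = 3–6%, the SARI hazard ratio shifts against the COVID one by 1.015/1.010 = 1.005 up to 1.12/1.04 = 1.077.

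**The case against.** The choice is documented and DAG-based, and the Aim 1 DAG figure is not available here, so the reasoning for each drug cannot be checked. Much of the possible confounding is already addressed: the model adjusts for cancer, asthma, COPD, rheumatoid arthritis or SLE, transplants, severe immunodeficiency and smoking. That stands, and it makes the upper figures above less likely. It does not close the matter, because these covariates are listed as diagnoses, without severity or current treatment.

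The retained immunosuppressant term might be meant to include steroids or chemotherapy. That is possible, but the separate list entries point the other way, and the text has to say which is meant.

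Some prescribing may follow from the neuropsychological disease, in which case leaving it out is defensible. The protocol does not give that reason for medications; its only stated ground is the lack of effect on COVID outcomes.

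Several stronger readings are tempting and are not supported:

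- That the omission pushes the hazard ratio away from 1. This needs positive drug associations with both exposure and outcome, and a true hazard ratio of at least 1. The Bias section expects some conditions to be protective, and an upward bias would move a hazard ratio below 1 towards 1.
- That the harm lies chiefly in the SARI cohort. The missing rationale is specific to SARI, but no figure shows a larger bias there. If the drugs matter for COVID too, the bias is shared and partly cancels.
- That the protocol's belief about COVID is shown to be wrong. Nothing in the document establishes that.
- That the sections flatly contradict each other. Listing variables and then selecting from them is consistent, and the Statistical Methods wording can be read together with the selection. It is loose rather than contradictory.

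**Conclusion.** The point holds as a gap in the justification and specification of the adjustment set. The stated reason for dropping these drugs covers one of the two outcomes analysed, the boundary of the immunosuppressant term is undefined, and two analysts could fit different Aim 1 models from the two sections. Following Effect Modifiers as written leaves candidate confounders out although they are listed variables, and no planned analysis would show whether that matters.

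That residual confounding is actually present is not demonstrated. The 1% to 8% range for one drug group rests wholly on assumed prevalences and effects, and comorbidity adjustment should reduce it. It is likely to be small, though in a cohort this large even a small bias can approach the random error if events are numerous. The change is worth making because it costs very little, not because a large bias has been shown.

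**What to change.** - **Effect Modifiers:** add baseline oral steroid, chemotherapy, radiotherapy and leukotriene/long-acting beta-agonist treatment to the Aim 1 adjustment set for cohorts 1 and 2. At minimum, pre-specify under Sensitivity analyses a model in both cohorts that adds them, and report the change in each hazard ratio and in the Objective 3 comparison.
- **Definition:** state whether oral steroids and chemotherapy count as immunosuppressants in the Aim 1 model.
- **Rationale:** replace the COVID-only reason with one that also covers SARI outcomes.
- **Statistical Methods, Aim 1:** refer explicitly to the resulting list, for both cohorts.

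The cost is a few extra terms built from variables already listed. There is a risk of slight over-adjustment if any of this prescribing follows from the neuropsychological disease; showing results with and without the added terms would make that visible.

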For cohort two, our primary outcome is the first occurrence of either hospital admission with SARI in the HES dataset (defined as a new ICD-10 code J09-J22 in the HES dataset) or ICU admission in the ICNARC CMP dataset with SARI (defined as any admission with unique diagnostic code any one of RE129 RE131 RE82 RE50 RE86 RE94 RE75 RE133 RE132 RE121 RE1 RE128 RE16 RE130 RE117 RE42 RE41) or death. Secondary outcomes will be each of these three events considered separately (I.e. SARI related hospital admission, ICU admission, death).

Aim 2.

Our primary outcome is development of new neuropsychological disease up to 1 year following hospital discharge which we define as having received a diagnostic code as below:

- Anxiety and stress-related disorders [ICD F40-48 and corresponding Read codes]
- Mood disorders [ICD F30-39 and corresponding Read codes]
- Psychotic disorders [ICD F20-29 and corresponding Read codes]
- Dementia [ICD F00-F03, G30, G31.0 ? and corresponding Read codes]

Secondary outcomes are the diagnosis of new neuropsychological disorders (as defined above) with treatment, and where numbers are available the new diagnosis with or without treatment of each class of disorders, each considered as a separate endpoint.

Neuropsychological treatments are defined as:

- Hypnotics and anxiolytics: (hypnotics, anxiolytics, barbiturates and methyprylone, benzodiazepines)
- Antidepressant drugs (Tricyclic and related antidepressant drugs, Monoamine-oxidase inhibitors, Selective serotonin re-uptake inhibitors, Other antidepressant drugs)
- Drugs used in psychoses and related disorders (Antipsychotic drugs and depot injections, Lithium salts, Phenothiazine derivatives)

Definition of exposures

Aim 1

Neuropsychological disease will be defined as an ordinal variable with the following three categories: no relevant diagnosis or drugs; diagnosis ever recorded without recent drug treatment; diagnosis present with recent drug treatment (with at least two prescriptions for neuropsychological treatments as above within the six months preceding study entry).

Our primary exposure is active neuropsychological disease on the study entry date which we define as having received a diagnostic code as above (24th January 2020 for cohort 1 and 24th January 2015 for cohort 2).

Aim 2.

The primary exposure is a hospital or ICU admission resulting from COVID-19 infection. Comparator exposures are hospital or ICU admission resulting from SARI.

Covariates

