Cause-specific Royston Parmar flexible parametric models will be used to estimate the hazard ratios of developing new neuropsychological diseases after having received intensive care, comparing patients who received intensive care for COVID-19 (cohort 3) vs those who received intensive care for SARI (cohort 4). This model will adjust for all previously listed covariates. The age variable will be included as a restricted cubic spline rather than a linear term. Follow-up will start on the date of discharge from hospital.

Proportional hazards assumption will be tested, and time dependent terms will be included if the hazard ratio changes over time. A random frailty term will be included to account for similarities amongst patients admitted in the same critical care unit

A limited number of two-way interactions which are considered to be clinically or biologically plausible will be identified prior to analysis, and tested using a Wald test.

Primary care data on some potential confounding variables is incomplete (e.g. smoking status, alcohol intake, ethnic group, BMI). Reason for admission is mandatory for all records in the ICNARC database (the core dataset for aim 2), so classification of these reasons as either SARI or COVID related will be non-missing for all patients. Only admission records for completed critical care stay (non-missing length of stay and survival status at end of critical care) will be included (n.b. outcomes are missing in <1% of COVID ICU admissions to date). Remaining variables from the critical care stay are use of sedation in the first 24 hours, and duration of advanced respiratory support, which are missing for a small number of patients (<1.5%).

Both aims.

To allow data analysis with all eligible patients, we will impute missing data in all cohorts. We will use multiple imputation with chained equations under the missing at random assumption to replace missing values and use these values in our main analyses [15]. We will include all exposure and confounding variables in the imputation model, along with the Nelson–Aalen estimator of the baseline cumulative hazard, and the outcome indicator. We will carry out five imputations. Analysis models will be fitted in each imputed dataset and Rubin's rules to will be used to combine the results across the imputed datasets.

As the analyses are on time to event data, patients will be censored at the date when they are lost to follow-up as defined in cohort definitions above.

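### The main Aim 2 model is to adjust for three ICU-course variables on a timing argument that is false for them, so its hazard ratio is not the overall COVID-19 versus SARI comparison

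*Protocol*

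**What the plan says.** Under Definition of exposures, Aim 2: "The primary exposure is a hospital or ICU admission resulting from COVID-19 infection", with SARI admission as comparator.

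Under Effect Modifiers, the Aim 2 paragraph takes ICU admission as the exposure. (It names SARI on both sides of the comparison; I read one side as COVID-19, in line with the exposure definition.) It says: "This exposure occurs at a fixed time which is used as the baseline for our time to event analysis", and that "all other variables listed above are measured before this baseline". From this it concludes that all listed covariates may go into the adjusted models, subject to sample size and event numbers.

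The covariate list just above ends with a group for the ICU stay, marked for Aim 2 only. It holds length of stay, duration of invasive ventilation and "Use of sedation in the first 24 hours of admission".

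Under Statistical Methods, Aim 2, the wording for the comparison of cohorts 3 and 4 is firm: "This model will adjust for all previously listed covariates". The same section starts follow-up at hospital discharge and describes how often sedation and ventilation duration are missing.

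The Aim 1 paragraph of Effect Modifiers leaves length of stay and sedation out of the model, "as these are outcomes potentially caused by Covid severity".

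**The concern.** The Aim 2 question is whether admission with COVID-19, rather than with another severe respiratory infection, is followed by more new neuropsychological disease. Length of stay, ventilation and sedation come after that admission and may depend on which infection the patient had. If they also affect later mental health, holding them fixed takes out whatever part of the difference runs through the ICU course. The model then answers a narrower question: how the groups differ among patients with the same length of stay, ventilation and sedation.

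Even that narrower answer needs control of whatever drives both the ICU course and the outcome. The covariate list has no measure of acute severity or physiology at admission. Conditioning on the ICU course can therefore create an association between infection type and unmeasured severity.

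At stake is the meaning of the main Aim 2 hazard ratio. A reader would take it as the overall COVID-19 versus SARI difference, and it would not be that.

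**Working it through.** There is no stated sample size, power or effect figure to reproduce. The main check is one of timing.

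**Step 1: order of events**

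| Event | When | Where stated |
|---|---|---|
| Demographics, lifestyle, comorbidity, prior medication | before admission | Covariates |
| Exposure: admission with COVID-19 or SARI | called the baseline | Effect Modifiers, Aim 2 |
| Sedation | first 24 hours after admission | Covariates, ICU stay |
| Ventilation duration, length of stay | accrue during the stay | Covariates, ICU stay |
| Start of follow-up | hospital discharge | Statistical Methods, Aim 2 |

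The three ICU variables come before discharge but after admission. The timing sentence holds if baseline means discharge and fails if baseline means the time of exposure, which is how that sentence defines it. Only variables from before the exposure can be admitted on the ground the paragraph gives.

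**Step 2: does the plan use them?** Effect Modifiers permits it; Statistical Methods commits to it. The discussion of missing sedation and ventilation data shows that they are meant as model variables. None of the listed sensitivity analyses (complete case, RNA-confirmed cases, earlier censoring, competing risk, weighting) is stated to drop them.

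**Step 3: what is the target?** Objective 5 compares the incidence of new disease after COVID-19 with that after SARI. The Introduction and the impact summary speak of allowing for prior neuropsychological disease, not for ICU course. No effect net of ICU course is stated.

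**Step 4: illustration only.** Let *s* be the COVID-19 minus SARI shift in one ICU-course variable, in standard deviations, and *h* the hazard ratio per standard deviation. Approximately

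overall HR = adjusted HR × h^s, so adjusted HR = overall HR / h^s.

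Neither *s* nor *h* is in the Protocol; both are assumed. For an overall HR of 1.20:

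| s | h^s, h = 1.2 | adjusted HR | h^s, h = 1.5 | adjusted HR |
|---|---|---|---|---|
| −0.3 | 0.947 | 1.27 | 0.885 | 1.36 |
| 0 | 1.000 | 1.20 | 1.000 | 1.20 |
| 0.3 | 1.056 | 1.14 | 1.129 | 1.06 |
| 0.6 | 1.116 | 1.08 | 1.275 | 0.94 |

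For example, 1.5^0.6 = 1.275 and 1.20 / 1.275 = 0.94.

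A single-run Cox simulation was used as a check. It took 11,000 patients against 35,000 (5 years × 7,000, from Study Size) and an assumed 10% one-year risk. Individual hazard ratios scatter, but the ratio of unadjusted to adjusted HR follows h^s. With direct HR 1.20, s = 0.6 and h = 1.5 it gave 1.619 / 1.280 = 1.265, against 1.275. With s = −0.3 and h = 1.5 it gave 1.057 / 1.212 = 0.872, against 0.885.

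The table leaves out bias from unmeasured severity, which could act in either direction.

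**The case against.** **The target is not written down.** Aim 2 speaks of associations, and the opening summary notes that sequelae are common after any critical illness and refers to accounting for risk factors. That is compatible with asking what COVID-19 adds beyond an equally intensive stay. This stands as far as it goes: the overall comparison is implied by Objective 5, not declared. But a direct effect is not declared either, and the reason given for including the three variables is their timing, not such a target.

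**The variables precede follow-up.** Correct. Nothing from after time zero enters the model. The fault is that exposure and time zero are treated as one baseline.

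**The wording is permissive.** It is under Effect Modifiers, but not in the description of the main model. The two need reconciling in any case.

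**The Aim 1 exclusion is a different setting.** A reader might infer a flat contradiction between the aims. The documents do not support that. In Aim 1 admission is part of the outcome, and the exclusion names length of stay and sedation, not ventilation. What carries over is the Protocol's own view that such factors may result from COVID-19 severity.

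**Cohorts 3 and 4 come from different periods.** Any difference in ICU course due to period rather than infection is not mediation. This stands, and is a reason to report both models.

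The Aim 2 causal diagram (Figure 4) is not visible and could bear on how these variables were classified. It could not make the timing sentence true.

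**Conclusion.** The point holds. The stated ground for the Aim 2 adjustment set is false for three variables, the main model is committed to them, and no planned analysis is stated to leave them out. The main hazard ratio would not be the overall COVID-19 versus SARI comparison implied by Objective 5, and it may be biased by unmeasured acute severity.

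A reader might go further and infer that the model hides a harmful effect of COVID-19. The documents do not support that. Attenuation needs COVID-19 stays to be longer or more intensive and this to raise risk, and the Protocol gives no figure for either. With no shift nothing is removed; with shorter COVID-19 stays the change reverses. The range of 0.94 to 1.36 around an overall HR of 1.20 shows only that the choice can matter. It rests wholly on assumed shifts of −0.3 to 0.6 SD and hazard ratios of 1.2 to 1.5 per SD.

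**What to change.** 1. Under Effect Modifiers, rewrite the Aim 2 timing sentence so that exposure (admission) and time zero (hospital discharge) are separate, and say that the three ICU-stay variables fall between them.
2. Reconcile the permissive wording there with the firm wording under Statistical Methods, Aim 2.
3. State that the primary Aim 2 target is the overall COVID-19 versus SARI difference.
4. Fit the primary model and the propensity score with the listed pre-admission covariates only: demographics, lifestyle, comorbidities and prior medication.
5. Report a second model that adds length of stay, ventilation duration and sedation, labelled as the difference not explained by ICU course.

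Prior neuropsychological history is a separate matter. The Introduction and the impact summary say it will be taken into account, but the covariate list does not contain it. If it is added, it should be described as an addition, not as part of restricting the set.

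Cost: a few sentences and one extra model. The drawback is a primary model with no marker of acute severity, which is why the second model should be shown beside it.
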